7.2.2 Reporting Serious Adverse Events

The investigator or designee must

- Complete a Serious Adverse Event Case Report Form in the subject's study record within 72 hours of recognition.
- Submit events that are a Serious Unexpected Suspected Adverse Reaction to the FDA within 15 calendar days of determining reportability
- Observe Emory University IRB Unanticipated Problem policy to determine events that meet requirements for immediate reporting. If an event meets the Emory University IRB requirements as an UP, the event will be submitted to the IRB and the DSMB. This timeframe also applies to additional new information (follow-up) on previously forwarded SAEs. Should the FDA or

national regulatory authorities require additional data on the event; the sponsor-investigator will ensure that those data are provided to the appropriate regulatory agencies in a timely fashion.

The following information about the patient and the event will need to be collected and available:

- Investigator identification
- Patient identification code (eg, sex, age, or date of birth)
- Information on study drug (eg, start/stop date, dose and frequency of study drug administered)
- Description of event

In addition to the above information, the sponsor will require the investigator's assessment of the following:

- Severity of the SAE
- Relationship of the SAE to the study drug
- Outcome of the SAE

7.2.3 Follow-up Information of Serious Adverse Events

Appropriate diagnostic tests should be performed and therapeutic measures, as medically indicated, should be instituted. Appropriate consultation and follow-up evaluations should be carried out until the event has resolved or is otherwise explained by the investigator. For all SAEs, the investigator is obligated to pursue and provide information to the appropriate regulatory agencies. There should be routine follow-up through and including 30 days after the last administration of assigned study treatment or the investigator/patient decision to discontinue treatment, whichever occurs later, in all patients in order to monitor for the occurrence of SAEs. If an SAE continues after the 30-day evaluation period, then the patient must be followed until the event resolves or returns to baseline. The medical monitor may specify a longer period of time if required to assure the safety of the patient.

7.3 Other Safety Issues

7.3.1 Pregnancy

Females of childbearing potential and fertile males will be informed as to the potential risk of conception while participating in this study and will be advised that they must use effective contraception from randomization through at least 30 days after the end of treatment. A pregnancy test will be performed on each pre-menopausal female of childbearing potential immediately prior to randomization, and again at the End-of-Treatment Visit. A negative pregnancy test must be documented prior to administration of study drug. If a patient is confirmed pregnant during the trial, study drug administration must be discontinued immediately. The investigator must immediately notify the appropriate regulatory agencies of this event and record the pregnancy on a Pregnancy Form. The investigator must immediately report follow-up information to the appropriate regulatory agencies regarding the course of the pregnancy, including perinatal and neonatal outcome, regardless of whether the patient has discontinued participation in the study. If the pregnancy results in the birth of a child, additional follow-up information may be requested. If the pregnancy results in spontaneous abortion or stillbirth, the event should be reported as an SAE. Pregnancy outcomes must be collected for the female partners of any males who took study drug in this study. Consent to report information regarding these pregnancy outcomes should be obtained from the female partner.

7.3.2 Overdose

An overdose is defined as the accidental or intentional ingestion or infusing of any dose of a product that is considered BOTH excessive AND medically important. All occurrences of overdose must be reported as an SAE. Monitor adverse events as instructed in the schedule of events and as clinically indicated.

7.4 Unanticipated Problems

Unanticipated problems (UPs) are events (adverse events or not) that will be assessed by the PI as unexpected, related to study participation, **and** involving risk for participants or others. A reportable event that fulfills all of these characteristics is considered an unanticipated problem.

To be unanticipated, the event should be unexpected, not described in the study documents, or if described before, it is now presenting with increased severity, duration, or frequency.

To be related to study participation, the event should be probably or possibly related to study participation, due to drug, or as a consequence of a study procedure (even if the procedure is considered standard of care). If an event could be explained by the underlying medical condition, it is not considered related.

To involve risk for participants or others, the event may affect subjects' risk. Even if the event did not result in harm, if the subject could have been affected by the event (safety, rights, welfare), the event is reportable.

Unanticipated problems will be report to the IRB using the reportable events form within 10 calendar days from the date the PI first learn about the event if the problem was unanticipated, related and involving risk to participants or others or if happening at increase frequency, duration or intensity that previously anticipated.

8. Statistical Considerations

8.1 General Considerations

For the purposes of this protocol and all analyses, a month of treatment is defined as 28 days, and will be the same length as a cycle of treatment for both groups.

8.2 Analysis Population

Intention to treat (ITT) population: The ITT population includes all patients who are randomized to the study. Patients will be analyzed according to the treatment to which they were assigned.

Safety Population: The safety population includes all patients who have received at least 1 dose of EACA. Patients included in the safety population will be analyzed according to the treatment they received.

Per-protocol Population: The per-protocol population includes all patients who are randomized, receive at least one dose of study drug, and have no major protocol violations that could be expected to impact response data, such as: failure to satisfy one or more eligibility criteria, administration of other anti-cancer therapy concurrent with study drug, and administration of incorrect study drug doses. Major protocol violations will be finalized and documented prior to final data analysis.

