All patients receiving at least 1 dose of study drug will be considered evaluable for safety. Patients will be analyzed for safety according to the treatment which they received. Listings of laboratory test results will also be generated, and descriptive statistics summarizing the changes in laboratory tests over time will be presented. Exposure to study drug over time will also be summarized. The AE incidence rates, as well as the frequency of occurrence of overall toxicity, categorized by toxicity grades (severity) will be described for each treatment arm and be compared between two arms using two-sided Chi-square test or t-test.

Quality of Life Analysis

Quality of life and health outcomes measures are being collected using EQ-5D-5L instruments before the study and at the end of the study. Means and medians of raw scores of these questionnaires will be summarized for each treatment group for each domain and be compared between the two arms with t-test or Wilcoxon ranks sum test.

Interim Analysis

Three interim analyses are planned after 11 patients in each arm have been randomized and their results have been obtained. Each interim analysis will focus on the primary endpoint, the proportion of patients with major bleeding ever noted during the study. To maintain an overall Type I error rate of 0.05 (1-sided), an O'Brien Fleming approach will be used which requires a 1-sided p-value < 0.001 at the first interim analysis (at 25% of total sample size). If this boundary is not crossed, then the study will continue and the second interim analysis will be conducted at 50% of the total sample size which requires a 1-sided significance level of 0.004. If this boundary is not crossed at the second interim analysis then, the study will continue and a third interim analysis will be conducted at 75% of the total sample size which requires a 1-sided significance level of 0.019. If this boundary is not crossed, the final primary analysis will be performed after completing 100% of the sample size using a 0.043 one-sided significance level.

TABLE OF CONTENTS

Protocol Synopsis

- 1. Background**
 - 1.1 Thrombocytopenia in Patients With Hematological Malignancies**
 - 1.2 Fibrinolysis and Inhibition of Fibrinolysis with Epsilon Aminocaproic Acid**
 - 1.3 Preliminary studies**
 - 1.4 Rationale for the study**
 - 2. Study Objectives and Hypothesis**
 - 2.1 Primary Objective**
 - 2.2 Secondary Objective**
 - 2.3 Hypothesis**
 - 3. Investigational Plan:**

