7.1.3 Performing Adverse Event Assessment

All observed or volunteered AEs, regardless of treatment group or suspected causal relationship to the investigational product, will be reported as described in the following sections. For all AEs, the investigator must pursue and obtain information adequate to determine the outcome of the AE and to assess whether it meets the criteria for classification as a serious AE requiring immediate notification to the appropriate regulatory agencies.

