7.1.4 Reporting Period

Serious Unexpected Suspected Adverse Reactions require notification of the appropriate regulatory agencies beginning from the time the patient provides informed consent, which is obtained prior to the patient's participation in the clinical study (ie, prior to undergoing any study-related procedure and/or receiving investigational product), through and including 30 days after the last administration of the assigned study treatment or the investigator/patient decision to discontinue treatment, whichever occurs later. Any SAE occurring any time during the reporting period must be reported to the FDA within 15 days of determining reportability if a causal relationship to the investigational product is suspected. Any SAE ongoing at the end of the reporting period should be followed as described below. For all enrolled patients, AEs (serious and non-serious) should be recorded on the eCRF beginning with the signing of the informed consent form and concluding 30 days following the last dose of the assigned study treatment or the investigator/patient decision to discontinue treatment, whichever occurs later. AEs ongoing after the reporting period: Any ongoing AEs thought to be at least possibly study-drug related and all ongoing SAEs after this time should be followed at least every 4 weeks until they resolve to baseline (or CTCAE grade \leq 1), stabilize, or are considered to be chronic/irreversible.

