8.3.2 Secondary Endpoint

Secondary endpoints include:

- proportion of patients with any bleeding during the study period in each arm
- the total number of units of platelets transfused in each arm at the end of the study
- Quality of life as measured by in each arm before the study and at the end of the study
- Safety in each arm

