8.5.3 Secondary Endpoint Analysis

One-sided t-test will be used to compare the total number of bleeding episodes noted during the study between the two arms. Two-sided t-test will be employed to compare the total number of units of platelets transfused at the end of the study between the two arms. Appropriate statistical tests (Chi-square test, t-test, Wilcoxon's rank sum test, etc.) will be conducted to compare the each score of the quality of life between the two arms before the study and at the end of the study, respectively. The change of each score of the quality of life from before the study to the end of the study will also be compared between the two arms. The safety in each arm will be also compared with Fisher's exact test. The analyses of secondary endpoints will be performed on the ITT population and the significance level will be kept at 0.05 for all tests.

For the primary and secondary efficacy endpoints, subgroup analyses will be performed by baseline potential prognostic factors. Subgroups will include: age, gender, race, underlying diagnosis, and other disease-related prognostic factors (disease status).

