8.6 Safety Analysis

All patients receiving at least 1 dose of study drug will be considered evaluable for safety. Patients will be analyzed for safety according to the treatment which they received. Listings of laboratory test results will

also be generated, and descriptive statistics summarizing the changes in laboratory tests over time will be presented. Exposure to study drug over time will also be summarized. The AE incidence rates, as well as the frequency of occurrence of overall toxicity, categorized by toxicity grades (severity) will be described for each treatment arm and be compared between two arms using two-sided Chi-square test or t-test.

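### The safety population admits only patients who took EACA, so the between-arm adverse event comparison in 8.6 has no platelet group, and 8.5.3 sets a different population and test for the same endpoint

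*Protocol*

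**What the plan says.** - **Population (8.2, repeated in the synopsis).** "The safety population includes all patients who have received at least 1 dose of EACA". Patients in this set are analysed by the treatment they received. No criterion admits a patient managed with platelets alone.
- **Safety analysis (8.6, repeated in the synopsis).** "All patients receiving at least 1 dose of study drug will be considered evaluable for safety", again grouped by treatment received. Adverse event incidence and toxicity by grade "will be described for each treatment arm and be compared between two arms using two-sided Chi-square test or t-test".
- **Safety as a secondary endpoint (3.3 and 8.3.2).** The list includes "Safety in each arm".
- **Secondary endpoint analysis (8.5.3, repeated in the synopsis).** "The safety in each arm will be also compared with" Fisher's exact test, with no sidedness given. "The analyses of secondary endpoints will be performed on the ITT population", at a significance level of 0.05. ITT in 8.2 means all randomised patients, as assigned.
- **Data collection (7.1.3 and 7.1.4).** "All observed or volunteered AEs, regardless of treatment group or suspected causal relationship to the investigational product, will be reported", and "For all enrolled patients, AEs (serious and non-serious) should be recorded on the eCRF". Section 6.3.1.2 also has adverse events during platelet infusions documented.

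**The concern.** A safety population in a two-arm trial has to contain both arms if it is to support a comparison. This one is defined by exposure to the experimental drug, so the control arm drops out by construction. The two-arm comparison in 8.6 then has nothing to compare against within the only population that the protocol names for safety.

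The second problem is duplication. The same endpoint is analysed in 8.5.3 and again in 8.6, with a different population, a different rule for assigning patients to groups and a different test. Neither analysis is marked as the main one. In an open-label trial, leaving that open allows the population and the test to be chosen after the adverse event data have been seen.

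What is at stake is the interpretation of adverse events. Table 1 of the protocol lists thrombosis and pulmonary embolism among the risks of EACA, and the withdrawal criteria in 5.4 anticipate thrombotic events on either arm. Without the platelet arm, a safety set cannot separate drug effects from the background rate in these patients.

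**Working it through.** **1. Who enters the set defined in 8.2**

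Inputs: 50 patients per arm (8.4), randomised 1:1 (3.5); entry on at least one EACA dose, grouped as treated (8.2).

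| Patient | Enters the 8.2 set? | Analysed under |
|---|---|---|
| EACA arm, took EACA | yes | EACA |
| EACA arm, never dosed | no | – |
| Platelet arm, never took EACA | no | – |
| Platelet arm, took EACA | yes | EACA |

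No row yields a patient analysed under platelets. If each arm is treated as assigned, the set holds up to 50 EACA and 0 platelet patients, against 50 v 50 on ITT. Crossover cannot supply a comparator, because of the as-treated rule. Patients re-enrolled under 5.3 are set aside here.

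**2. Does 8.6 escape through its own wording?**

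Section 8.6 speaks of study drug and does not name the safety population. Section 5.4 glosses study drug as EACA in its rule on treatment interruption, and 6.5.3 describes study drug as tablets dispensed by the pharmacy.

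- Narrow reading (study drug is EACA): 8.6 inherits the empty platelet group.
- Broad reading (either assigned treatment): 8.6 has two arms, but its evaluable set is no longer the one in 8.2.

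Either way, the sections do not agree.

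**3. The two rules for one endpoint**

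| | 8.5.3 | 8.6 |
|---|---|---|
| Population | ITT | at least one dose of study drug |
| Grouping | as assigned | as received |
| Test | Fisher's exact, sidedness not stated | two-sided chi-square or t-test |

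**4. Can the choice of test change a conclusion?**

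The protocol gives no figure for this. Assume 50 v 50, a two-sided Fisher test and a 0.05 level. There are 51 × 51 = 2,601 possible tables for one adverse event term.

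Worked example, 5/50 v 0/50 (assumed counts):

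- Fisher: one tail = C(50,5)/C(100,5) = 2,118,760/75,287,520 = 0.0281; both tails = 0.056.
- Uncorrected chi-square: 100 × (5×50 − 45×0)² / (50×50×5×95) = 6,250,000/1,187,500 = 5.263; p = 0.022.
- Yates-corrected: 100 × (250 − 50)² / 1,187,500 = 3.368; p = 0.066.

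The minimum expected count in this table is only 2.5, but sparse cells are not needed for a disagreement:

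| Events | Fisher | Uncorrected | Yates | Minimum expected |
|---|---|---|---|---|
| 9 v 2 | 0.051 | 0.025 | 0.055 | 5.5 |
| 12 v 4 | 0.054 | 0.029 | 0.056 | 8.0 |

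Over all 2,601 tables:

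- Fisher v Yates-corrected chi-square: 0 disagreements.
- Fisher v uncorrected chi-square: 94 disagreements, every one with chi-square significant and Fisher not. In 82 of the 94 the minimum expected count is at least 5.

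The exact binomial probability of a Fisher v uncorrected disagreement for one term is the sum, over the 94 tables, of the product of the two arms' binomial probabilities:

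| Assumed true rates | Probability |
|---|---|
| 5% both arms | 3.6% |
| 10% both | 3.3% |
| 20% both | 2.4% |
| 30% both | 1.9% |
| 50% both | 2.2% |
| 40 v 20% | 8.0% |
| 30 v 15% | 8.8% |
| 30 v 10% | 9.4% |
| 20 v 5% | 15.6% |
| 10 v 2% | 19.2% |

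**The case against.** The strongest reply is that the intent is clear. Grouping by treatment received has no function in a one-treatment set, 8.6 plainly expects two arms, and adverse events are collected in both. Section 8.6 carries its own evaluability rule, and 5.4 uses study drug loosely enough to apply to events on either arm. On that reading the defect is a single word in 8.2. The ITT comparison in 8.5.3 already works, and the word also in its safety sentence may mean that an additional analysis was intended.

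Much of this is fair. The EACA-only wording does look like a drafting slip, and nothing is irretrievable. But the broad reading does not reconcile the sections; it turns 8.6 into a contradiction of 8.2. If two safety analyses were meant, neither is identified as the main one. A statistical analysis plan may fill in detail, but these are two rules that the protocol itself states, and they conflict.

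The objection is stronger on the tests. The disagreement depends on an uncorrected chi-square, which the protocol does not specify, on a two-sided Fisher test, and on assumed event rates. It is a subsidiary point and does not measure the population defect.

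Two comments on the remedy also stand. An as-treated rule needs to say what happens to a crossover's events before the first EACA dose. The per-protocol population in 8.2 uses the same study-drug condition and should be clarified at the same time.

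**Conclusion.** The concern holds and should be fixed before analysis. Under the written definitions the safety population contains up to 50 EACA patients and no platelet patients, so the comparison in 8.6 cannot be carried out on it. This follows from the text and depends on no assumption about event rates. The only two-arm safety comparison that works as written is the ITT one in 8.5.3, which uses a different grouping rule and a different test.

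The conflict between tests is real but smaller and conditional. If the chi-square is uncorrected and Fisher is two-sided at 50 v 50, the two disagree for a given adverse event term with probability of about 2–4% at equal true rates of 5–50%, and about 8–19% at the unequal rates assumed above. With a Yates correction they never disagree. The protocol does not say whether a correction applies.

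The primary endpoint analysis, the sample size and data collection are unaffected.

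**What to change.** - **8.2 and synopsis.** Define the safety population as all randomised patients who, after randomisation, either received at least one dose of EACA or were managed under prophylactic platelet transfusion, whether or not a transfusion was needed. Analyse by treatment received: anyone who took EACA counts under EACA, all others in the set under platelets. State how a crossover's events before the first EACA dose are handled.
- **Start of platelet management.** Use the randomisation date, since 5.1 places randomisation immediately before assigned treatment begins. List separately any randomised patient who had neither treatment.
- **8.5.3, 8.6 and synopsis.** Refer to this one population and name one test for adverse event incidences, with its sidedness. Two-sided Fisher's exact is one option, since 8.5.3 already names Fisher; any single named test removes the conflict.
- **ITT safety comparison.** If it is kept alongside, say which analysis is the main one. Labelling ITT as supportive would be consistent with the as-treated rule.
- **Per-protocol population in 8.2.** State whether study drug there includes the platelet arm.

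The cost is wording in 8.2, 8.5.3, 8.6 and the synopsis. No new data are needed, because adverse events are already recorded in both arms, and the sample size does not change.

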8.3 Study Endpoints

8.3.1 Primary Endpoint

The primary objective of this study is to compare at the end of the study, the proportion of patients with major bleeding during the study period among patients randomized to receive either EACA or standard of care prophylactic platelet transfusions.

8.3.2 Secondary Endpoint

Secondary endpoints include:

- proportion of patients with any bleeding during the study period in each arm
- the total number of units of platelets transfused in each arm at the end of the study
- Quality of life as measured by in each arm before the study and at the end of the study
- Safety in each arm

8.4 Determination of Sample Size

This randomized, open-label phase II study is designed to compare proportion of patient with bleedings noted during the study. Patients will be assigned to receive prophylactic EACA (experimental arm) or prophylactic platelet (standard of care) in a 1:1 fashion. Previous studies suggest that the proportions of patients with major bleeding will be expected to be 8% and 30% in experimental arm and standard of care arm, respectively. With one sided Fisher's exact test, the sample size of 45 patients in each arm will achieve a power of 80% at the significance level of 5% to test whether prophylactic EACA can prevent major bleeding better than the standard of care. After adjusting for a 10% drop out rate, the actual required sample size will be 50 patients per arm. Therefore, the total sample size of the study will be 100 patients.

